### 8.3.3. Analysis of Heterologous Strains

HAI and Neut antibody responses against antigenically drifted variants of influenza A/H7 viruses, A/Shanghai/2/2013 and A/Guangdong/17SF003/2016, will be summarized for the Per Protocol population as described in Section 8. Results will be presented in [Table 44](#) and [Table 45](#) for A/Shanghai/2/2013 and in [Table 46](#) and [Table 47](#) for A/Guangdong/17F003/2016. A scatter plot of the correlation between response to the vaccine strain and each heterologous strain will be presented in [Figure 23](#), [Figure 24](#), [Figure 25](#), and [Figure 26](#). No formal hypothesis testing or modeling for the exploratory analysis of heterologous strains is planned.

### 8.3.4. NA Serum Antibody Responses

Descriptions of the NA assays and planned analyses will be described in an addendum to this SAP.

---

## 9. SAFETY EVALUATION

All summaries and analysis of safety data will be presented for the safety population. Safety summaries will be presented overall and grouped by study group and stratum.

Continuous variables will be summarized using the following descriptive statistics: n (non-missing sample size), mean, standard deviation, median, maximum and minimum. All categorical measures will be summarized by the frequency and percentages of observed levels. The denominator for the percentages may be based on the number of non-missing observations for an assessment or based on the number of subjects in a population. This will be described for each table.

### 9.1. Demographic and Other Baseline Characteristics

Summaries of age, sex, ethnicity, race, BMI, and prior receipt of seasonal influenza vaccine will be presented by site in [Table 17](#) and [Table 18](#) and by study group and stratum in [Table 19](#) and [Table 20](#). Age will be summarized as a continuous variable as well as by categories as defined in Section 8.3.1. Ethnicity is categorized as Hispanic or Latino, or not Hispanic or Latino. In accordance with NIH reporting policy, subjects may self-designate as belonging to more than one race or may refuse to identify a race, the latter reflected in the electronic case report form (eCRF) as “No” to each racial option. BMI will be summarized as continuous as well as categorical, categorized as (<30, ≥30). Self-reported history of prior receipt of seasonal influenza vaccine will be categorized as follows: both 2017-2018 and 2018-2019, 2017-2018 only, 2018-2019 only, receipt of none, or unknown. Demographic information for individual subjects will be provided in [Listing 6](#).

#### 9.1.1. Prior and Concurrent Medical Conditions

All current illnesses and past or pre-existing medical conditions will be coded using Medical Dictionary for Regulatory Activities (MedDRA®) version 20.0 or higher.

Summaries of subjects’ prior and concurrent medical conditions will be presented by study group and stratum in [Table 21](#).

Individual subject listings will be presented for all reported medical history including prior and concurrent medical conditions in [Listing 7](#).

#### 9.1.2. Prior and Concomitant Medications

Concomitant medications will be coded to the Anatomical Therapeutic Classification using the WHO Drug Dictionary. The use of concomitant medications during the study will be summarized by ATC1 and ATC2 code, study group, and stratum for the safety population in [Table 85](#). A listing of concomitant medications will be presented in [Listing 18](#).

### 9.2. Measurements of Treatment Compliance

All subjects who were enrolled but not vaccinated will be presented by study group and stratum as part of the subject disposition in [Table 14](#). Subjects receiving investigational product will be presented by site, stratum, and study group in [Table 16](#). [Listing 1](#) presents subjects who received investigational product with randomized study group, study product received, and stratum.

### 9.3. Adverse Events

A summary of all adverse events is provided in [Table 48](#). A summary of those events that occurred in  $\geq 5\%$  if subjects in any study group and stratum combination is provided in [Table 49](#).

#### 9.3.1. Solicited Events and Symptoms

Systemic solicited adverse events will be collected pre-vaccination and systemic and injection site solicited adverse events will be collected approximately 20 minutes post-vaccination and then daily for 7 days after study vaccination. Systemic events include fever, feverishness, fatigue, malaise, myalgia, arthralgia, headache and nausea and the grading scale for systemic events, including quantitative grading for fever is found in [Table 10](#). Injection site events include injection site pruritus, injection site ecchymosis, injection site erythema, injection site induration/swelling, injection site pain and injection site tenderness. Ecchymosis, erythema and induration at the injection site are evaluated using both functional grade and measurement grading scales as defined in [Table 9](#).

When calculating the incidence of solicited events, each subject will be counted once at the highest severity and any repetitions will be ignored. When presenting solicited event summaries, the denominator for percentages will be the number of subjects who received the study vaccination with non-missing data for the event summarized.

The number and percentage of subjects reporting at least one solicited adverse event of any severity will be summarized for each solicited symptom, any systemic symptom, any injection site symptom and any symptom. For each event, the denominator is the number of subjects who received the study vaccination with non-missing data for the specified event. The 95% CI calculated using Clopper-Pearson methodology from a binomial distribution (SAS Proc Freq with a binomial option) will be presented in [Table 50](#).

For each systemic event, each local event, any systemic event, any injection site event, and any solicited event, the maximum severity over 7 days after study vaccination will be summarized for the safety population. The number and percentage of subjects reporting each event will be summarized by the maximum severity, study group, and stratum. For each event the denominator is the number of subjects who received the study vaccination with non-missing data for the specific event. The 95% CI calculated using Clopper-Pearson methodology from a binomial distribution (SAS Proc Freq with a binomial option) will be presented in [Table 51](#).

The number of subjects reporting a solicited adverse event will be summarized for each day post vaccination as a summary in [Table 52](#) and graphically in a bar chart in [Figure 26](#) for systemic symptoms and [Figure 27](#) for local symptoms.

Systemic and injection site solicited events reported by subject will be presented in [Listing 11](#) and [Listing 12](#), sorted by subject ID, parameter, and study day.

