Vital signs (oral temperature, pulse and blood pressure [BP]) will be collected at the screening visit (optional) and prior to study vaccination. Vital signs may be obtained if indicated at approximately 1, 3 and 7 days after study vaccination (this may only occur approximately 7 days after study vaccination for sites not processing blood for PBMCs isolation). Vital signs assessed on Day 1 prior to study vaccination will be considered as baseline. Subjects must not eat or drink anything hot or cold, or smoke within 10 minutes prior to taking oral temperature.

Height and weight will be collected at the screening visit (optional) or on Day 1 prior to study vaccination for the calculation of BMI.

Reactogenicity assessments will include an assessment of solicited AEs occurring from the time of study vaccination through 7 days after study vaccination, which includes an assessment of

injection site reactions including pruritus, ecchymosis, erythema, induration, edema, pain, and tenderness as well as systemic reactions including fever, feverishness, fatigue, malaise, myalgia, arthralgia, headache, and nausea. Pre-administration reactogenicity assessments will be performed immediately prior to study vaccination to establish baseline, then the study vaccination will be given.

Subjects will be observed in the clinic for at least 20 minutes after study vaccination. The study vaccination site will be examined, post-administration reactogenicity assessments will be performed, and any AE/SAEs will be recorded on the appropriate DCF prior to discharge from the clinic. The study vaccination site will also be examined approximately 1, 3 and 7 days after study vaccination (this will only occur approximately 7 days after study vaccination for sites not processing blood for PBMCs isolation).

All subjects will complete a Memory Aid from the time of study vaccination through 7 days after study vaccination. Memory Aids will be reviewed with the subjects for any AEs (solicited injection site and systemic reactions as well as unsolicited AEs), SAEs and concomitant medications (including solicitation for receipt of any non-study influenza vaccines) approximately 1, 3 and 7 days after study vaccination via phone call or clinic visit.

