9.2 Methods and Timing for Assessing, Recording and Analyzing Safety Parameters

9.2.1 Adverse Events

Adverse Event (AE): ICH E6 GCP defines an AE as any untoward medical occurrence in a patient or clinical investigation subject administered a pharmaceutical product regardless of its causal relationship to the study treatment. The FDA defines an AE as any untoward medical occurrence associated with the use of a drug in humans, whether or not considered drug related.

An AE can therefore be any unfavorable and unintended sign (including an abnormal laboratory finding), symptom or disease temporally associated with the use of a medicinal (investigational)

product. The occurrence of an AE may come to the attention of study personnel during study visits and interviews of a study recipient presenting for medical care, or upon review by a study monitor.

AEs, including solicited injection site and systemic (subjective and quantitative) reactions, not meeting the protocol-defined criteria for SAEs, will be recorded on the appropriate DCF and entered into the eCRF. Information to be collected for unsolicited non-serious AEs includes event description, date of onset, licensed study physician's assessment of severity and relationship to study product or alternate etiology (if not related to study product) (assessed only by those with the training and authority to make a diagnosis and listed on the Form FDA 1572 as the site PI or sub-investigator), date of resolution, seriousness, and outcome. AEs occurring during the trial-collection and reporting period will be documented appropriately regardless of relationship to study product. AEs will be followed through resolution.

Any medical condition that is present at the time that the subject is screened will be considered as baseline and not reported as an AE. However, if the severity of any pre-existing medical condition increases, it will be recorded as an AE.

AEs must be assessed for severity and relationship to study product (see definitions below). AEs characterized as intermittent require documentation of onset and duration of each episode. The start and stop date of each reported AE will be recorded on the appropriate DCF and entered into the eCRF.

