#### **3.2. Endpoints**

##### **3.2.1. Primary**

###### Safety

- Occurrence of all serious adverse events (SAEs) from the time of study vaccination through approximately 12 months after study vaccination.

- Occurrence of solicited injection site and systemic reactogenicity events from the time of study vaccination through 7 days after study vaccination.
- Occurrence of clinical safety laboratory AEs from the time of study vaccination through approximately 7 days after study vaccination.

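### A systemic symptom present before the dose and unchanged after it counts as a solicited reaction, because no counting rule in SAP 9.3.1 uses the pre-vaccination baseline

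*SAP*

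**What the plan says.** **Baseline.** Protocol 7.1: "Pre-administration reactogenicity assessments will be performed immediately prior to study vaccination to establish baseline". SAP 9.3.1 confirms the collection: "Systemic solicited adverse events will be collected pre-vaccination".

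**Counting.** SAP 9.3.1 states that "each subject will be counted once at the highest severity and any repetitions will be ignored". For Table 50: "The number and percentage of subjects reporting at least one solicited adverse event of any severity will be summarized for each solicited symptom". For Table 51, "the maximum severity over 7 days after study vaccination will be summarized for the safety population". None of these sentences compares a grade with the subject's own pre-vaccination grade. The analysis paragraph in Protocol 11.6.2 does not either: it takes the worst response over follow-up and splits it into none versus any grade. Topline Table 48 has a row for subjects with at least one systemic solicited event, also without a baseline condition.

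**Endpoint.** SAP 3.2.1, as in the protocol: "Occurrence of solicited injection site and systemic reactogenicity events from the time of study vaccination through 7 days after study vaccination".

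**General AE rule.** Protocol 9.2.1 includes solicited reactions among AEs and says: "Any medical condition that is present at the time that the subject is screened will be considered as baseline and not reported as an AE". Its next sentence makes an increase in severity an AE.

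**Display of the baseline.** Pre-vaccination symptoms have a separate column in Table 52, as counts by grade and group.

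**The concern.** A grade recorded before the dose serves to separate what the vaccine caused from what the subject arrived with. The plan collects that grade for systemic symptoms and then does not use it to decide what counts. A subject with mild arthralgia before the dose and the same mild arthralgia on later days is scored as having a mild solicited reaction.

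Such subjects are foreseeable. Exclusion criterion 1 admits people with minor residual symptoms of a nearly resolved illness, and inclusion criterion 6 admits stable chronic conditions with as-needed medication.

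At stake are the systemic rates of a primary safety outcome, including a topline row, and the descriptive contrast between AS03 and no AS03. Background symptoms raise both rates. They raise the lower rate more, because fewer of those subjects would have been counted anyway.

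**Working it through.** **1. The plan's own figures.** None depends on the baseline rule. The nearest are SAP Tables 5 and 6, and they reproduce. For Table 5, 1-(1-0.10)^30 = 95.76% (printed 95) and 1-(1-0.01)^210 = 87.88% (printed 87). For Table 6, the Clopper-Pearson interval at 50% is 35.5-64.5 for N=50 and 43.0-57.0 for N=210, in line with the printed 35-65 and 43-57.

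**2. Three kinds of record for one systemic symptom.**

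| Before dose | After dose | Tables 50 and 51 as written | Under a new-or-worsened rule |
|---|---|---|---|
| none | mild | counted, mild | counted, mild |
| mild | mild | counted, mild | not counted |
| mild | moderate | counted, moderate | counted, moderate |

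Only the second row differs. It is the case where Protocol 9.2.1, if it governs solicited symptoms, would not record an AE.

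**3. Effect on the rates.** Let p be the true reaction rate and b the share of subjects with a baseline symptom that persists after the dose. Assume that b is equal in both arms and independent of true reactions.

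- Reported rate = 1-(1-p)(1-b) = p + b(1-p)
- Reported difference = (1-b) × true difference
- Extra subjects in an arm of 210 = 210 × b(1-p)

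The arm size of 210 follows from 420 subjects randomised 1:1. The documents give neither b nor systemic reaction rates for this trial, so the values below are assumptions. In each pair, the first figure is without AS03.

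| True rates | b | Reported rates | Difference (points) | Extra per 210 |
|---|---|---|---|---|
| 30%, 60% | 1% | 30.7%, 60.4% | 29.7 (true 30.0) | 1.5, 0.8 |
| 30%, 60% | 5% | 33.5%, 62.0% | 28.5 | 7.4, 4.2 |
| 30%, 60% | 10% | 37.0%, 64.0% | 27.0 | 14.7, 8.4 |
| 20%, 30% | 1% | 20.8%, 30.7% | 9.9 (true 10.0) | 1.7, 1.5 |
| 20%, 30% | 5% | 24.0%, 33.5% | 9.5 | 8.4, 7.4 |
| 20%, 30% | 10% | 28.0%, 37.0% | 9.0 | 16.8, 14.7 |

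**4. What a new-or-worsened rule recovers.** Suppose a subject with a baseline symptom shows a visible worsening with half the chance p. The rate is then (1-b)p + b × p/2. For true rates of 20% and 30%:

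- b = 5%: 19.5% and 29.25%, difference 9.75 points.
- b = 10%: 19.0% and 28.5%, difference 9.5 points.

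The upward shift is gone and half of the lost difference returns. The rest is lost because a mild reaction over a mild baseline symptom cannot be seen.

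**5. Illustrative power.** For 20% versus 30% at 210 per arm, two-sided 0.05, power is 65.9% with no baseline symptoms. At b = 5% it is 57.6% as written and 64.4% under the rule in step 4. At b = 10% it is 50.4% and 62.9%. SAP 9.3.1 plans no such test, so this only gives a scale.

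**6. Symptoms outside the problem.** Injection-site symptoms have no source before the injection. Entry requires an oral temperature below 100.0°F and grade 1 fever starts at 100.4°F, so an eligible subject cannot have graded fever at baseline.

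**The case against.** **The time window.** A reader might infer from the Table 50 sentence, read with "Systemic solicited adverse events will be collected pre-vaccination and systemic and injection site solicited adverse events will be collected approximately 20 minutes post-vaccination", that a headache present before the dose and gone afterwards also counts, and that Tables 50 and 51 will therefore disagree. The documents do not support this. The endpoint starts at vaccination, SAP 4.5.1 repeats that window, Protocol 11.6.2 works on post-vaccination days, and SAP Section 12 declares no change from the protocol's analyses. The missing window in the Table 50 sentence is missing detail, not a different rule.

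**Counting all post-vaccination reports is legitimate.** Protocol 11.6.2 sets no baseline condition, and randomisation makes the background equal in expectation. This stands as a reason to keep the all-reports summary. It does not remove the effect: an equal background b adds b(1-p), which is larger where p is smaller, so it does not cancel in the difference. A new-or-worsened rule also has a bias of its own, towards under-counting mild reactions, so it should not simply replace the present summary.

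**Protocol 9.2.1 speaks of medical conditions at screening.** It may not have been written for solicited symptoms. That is fair, and the misfit is an unreconciled gap rather than a flat contradiction. But the same section includes solicited reactions among AEs, and SAP 9.3.1 does not say whether the rule applies to them.

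**The size is assumed and small.** This stands. If b is read as the prevalence of any baseline symptom, the table is an upper bound: it requires every such symptom to persist and none to occur in subjects who would have reacted anyway. At 30% versus 60% and b = 5%, the 1.5-point loss is well inside the plan's precision at N=210 (43-57).

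**Subject-level data exist.** Listing 11 is by subject and may allow manual linkage, though it does not explicitly name pre-vaccination rows. The Table 52 column alone cannot separate persisting from worsened symptoms.

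**Conclusion.** The point holds for one kind of record: a systemic symptom present before the dose and continuing at the same grade. It is counted at full grade in Tables 48, 50 and 51, although a baseline was collected and Protocol 9.2.1 would count only an increase.

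The direction follows from the algebra: rates up in both arms, AS03 difference down. For b of 1% to 10% and true rates of 20% to 60%, the rise is 0.4 points (0.01 × 0.40) to 8.0 points (0.10 × 0.80), and the difference loses 1% to 10% of itself. This rests on equal b in both arms and independence from true reactions. If b is near zero, the effect is near zero.

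A reader might go further and conclude that the reported rates will be materially inflated or that the AS03 comparison is compromised. The documents give no baseline prevalence and SAP 9.3.1 specifies no between-arm test, so neither conclusion is supported. The plan should still be changed, because the outcome is primary and the data needed are already collected.

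**What to change.** In SAP 9.3.1 and the table shells:

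1. State that Tables 48, 50 and 51 use only records from vaccination through Day 8.
2. Keep the all-reports summary. Beside Tables 50 and 51, add a version for systemic symptoms that counts a symptom only if it was absent before the dose or its post-vaccination grade exceeds the subject's pre-vaccination grade.
3. State how Protocol 9.2.1 applies to solicited events.
4. Keep the pre-vaccination column of Table 52.

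The cost is SAP wording and a little extra programming, with no new data. The new-or-worsened version misses a mild reaction on top of a mild baseline symptom, which is why both versions should be shown.

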#### 9.3.2. Unsolicited Adverse Events

When calculating the incidence of unsolicited AEs (i.e., on a per subject basis), each subject will only be counted once at the highest severity and/or relationship, and any repetitions of AEs within a subject will be ignored. The denominator for these summaries will be the total number of subjects in the Safety population. All AEs reported will be included in the summaries and analyses.

The number and percentage of subjects reporting at least one unsolicited AE in each stratum and study group will be summarized by MedDRA system organ class (SOC) and preferred term (PT). A 95% CI will be

presented for the percentage of subjects reporting any unsolicited event (serious or non-serious) for each MedDRA SOC and PT in [Table 53](#).

The following summaries for unsolicited AEs will be presented by MedDRA SOC, PT, study group, and stratum:

- Incidence of AEs by severity and relationship to study product in [Table 54](#);
- Incidence of non-serious, related AEs by severity in [Table 55](#);
- Incidence of AEs over time (Days 1-8, Days 9-22 post study vaccination) in [Table 56](#);
- Incidence of non-serious, related AEs over time (Days 1-8, Days 9-22 post study vaccination) in [Table 57](#) – note this table presents results for the secondary safety endpoint, “Occurrence of study vaccine-related unsolicited non-serious AEs from the time of study vaccination through approximately 21 days after study vaccination”;
- Total frequency of AEs over time (Days 1-8, Days 9-22 post study vaccination) in [Table 58](#);
- Subject listing of non-serious AEs of moderate or great severity in [Table 63](#);
- Bar chart displaying total frequency of AEs by severity, MedDRA SOC, study group, and stratum in [Figure 28](#);
- Bar chart displaying incidence of AEs by severity, MedDRA SOC, study group, and stratum in [Figure 29](#);
- Bar charts displaying total frequency and incidence of AEs by relationship to study product, MedDRA SOC, study group, and stratum in [Figure 30](#) and [Figure 31](#), respectively;

